**THE SPONSOR OR ITS DESIGNEE MUST BE NOTIFIED OF A SUBJECT WITHDRAWAL.**

### **13.3. SUBJECT EXIT**

Subject exit and termination forms must be completed for all subjects who signed informed consent and either complete the study, discontinue participating in the study, are considered lost to follow-up, or are withdrawn from the study. Before a subject is considered "lost to follow-up", there must be at least two documented attempts to contact the subject.

## **14. ASSESSMENTS OF MOTUS CLEANSING SYSTEM (MCS)**

The first 3 subjects of each physician will be excluded from the MCS performance evaluation in order to compensate for the system operation learning curve. Those subjects however will be included in the safety evaluation.

### **14.1. PERFORMANCE ASSESSMENT**

The rate of adequate cleansing level before and after the cleansing operation will be evaluated.

The rating of the cleansing quality will be evaluated by using the Boston Bowel Preparation Scale (BBPS) (Appendix A). Segment score of 0-3 given to each of the 3 segments of the colon (Left side, Transverse and right side).

BBPS\* scores will be rated by the colonoscopies, on the basis of three segment scores summed for maximum score of 9, where:

- 0 = unprepared
- 9 = completely clean (in completed to Cecum procedures)

An adequate cleansing procedure will be considered when all the colon segments will be graded as 2 or above.

Note: the above is applicable also for an incomplete procedures.

\* Detailed information is provided in Appendix A.

#### 14.1.1. PRE- PROCEDURE CLEANSING PER SUBJECT

Evaluating the cleansing (preparation) rate while inserting the device, prior to the cleaning procedure, for the entire colon.

This measurement will serve as the subjects' baseline condition with regards to colon cleansing.

#### 14.1.2. POST PROCEDURE CLEANSING PER SUBJECT

Evaluating the cleansing rate of the MCS while withdrawing colonoscope, post the cleaning procedure, for the entire colon.

### 14.2. SAFETY ASSESSMENT

An independent group of experts chosen by the sponsor will constitute the Data and Safety Monitoring Board (DSMB). The DSMB will evaluate every Adverse Event. All Adverse Events will be reported as per the standard clinical practices, according to section 16.3. All adverse event incidence rates will be summarized by anticipation, severity and relationship to the investigational device.

The incidence of major complications using the MCS and the Standard Optical Colonoscopy will be presented.

The safety of the MCS in terms of rate of MCS -related severe adverse events as compared to standard colonoscopy procedure will be evaluated. Overall, routine colonoscopy is considered to be a safe procedure with an overall low risk of major complications of approximately 0.35 percent. Expected (non-severe) adverse events which is under estimated due to the lack of monitoring those events in literature, include device related mucosal trauma, changes in bowel habits, nausea, bloating, abdominal discomfort, gas and in some cases bleeding.

Mild anticipated incidents, seen also in a standard colonoscopy with no clinical significant meaning, will be reported as per the direction of the DSMB.

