##### **4.2. ANTICIPATED ADVERSE DEVICE EFFECTS**

The potential complications associated with the MCS device are:

- Perforation
- Laceration
- Mild tissue trauma
- Patient infection/biologic reaction

Several steps to mitigate those risks were made (see section 4.3) , following those mitigations the use of the MSC do not increase the risk to the patient.

However as the MCS is used in conjunction with a standard colonoscope during a colonoscopy procedure the complications associated with using the MCS cannot be differentiated from those associated with the colonoscopy procedure.

The risks associated with the colonoscopy procedure along with the procedure itself (i.e., preparation and sedation) as reported in the literature are:

- Colonoscopy-related risk such as bowel perforation, tissue trauma, abdominal pain, bleeding, fever, and infection.
- preparation related risks (lasting >24 hours following colonoscopy) are: Changes in bowel habits, Nausea and vomiting, Dehydration and Renal dysfunction (rare).
- Sedation-related are: cardiovascular disorder, hypotension, and hypoxia
- Death

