#### **4.6. STEPS THAT WILL BE TAKEN TO CONTROL/ MITIGATE THE RISK**

In order to ensure the safety of the MCS device for subjects enrolled in the study an independent group of experts chosen by the sponsor will constitute the Data and Safety Monitoring Board (DSMB). The DSMB will evaluate every Adverse Event. All Adverse Events will be reported as per the standard clinical practices as detailed in section 16.3. All adverse event incidence rates will be summarized by anticipation, severity and relationship to the investigational device.

In addition, in case of occurrence of a SAE at least possibly related to the MCS the study will be terminated immediately and until completion of the DSMB investigation.

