#### **4.7. RISK/BENEFIT RATIONALE**

The MCS is used in conjunction with a standard colonoscope during a colonoscopy procedure. Hence, the complications associated with using the MCS are anticipated to be similar to those associated with the colonoscopy procedure. As with any colonoscopy procedure, when using the MCS there is some risk of bowel perforation, pain, infection and bleeding. Although the risks of the procedure with the MCS is expected to be comparable to conventional colonoscope (0.35%), the device is an add-on to a standard colonoscope. Hence, diameter is bigger, and the cleansing time may add some minutes to the procedure time. In contrast, a disadvantage that is presented in standard colonoscopy and can possibly be decreased when using the MCS is that of stopping the colonoscopy procedure due to improper preparation of the colon by the subject.

The potential benefits of the MCS are utilization of a cleaning technology that may improve the standard colonoscopy visualization, reduce reliance on subject pre-procedure colon preparation for ensuring high quality colonoscopy, increase the subject compliance to colonoscopy procedure and reduce the need for repeated colonoscopies required due to insufficient colon preparation, these consequently may reduce pain, discomfort, risk and cost.

The latest MCS version was tested in an animal study including 35 pigs and two preliminary clinical studies including 30 subjects. No major complication or serious adverse events occurred within the course of those studies, and only 2 mild adverse events were reported .

In addition, these clinical studies demonstrated an excellent cleansing effectiveness; MCS improved the cleansing level from 30% at baseline to 93% after the cleansing was operated, where preparation was identical to the current study. Efficacy results support the study design rationale that decreases the risks associated with the preparation without increasing the risk related to incomplete colonoscopy procedure.

Lastly, patients to be enrolled to this study shall be eligible to colonoscopy, thus the risks detailed above covers all the population intended to participate in the study (i.e., screening, surveillance and diagnostic).

Considering the residual risks and the potential and the risk against benefit assessment, it can be concluded that the system may offer potential benefit to the patients along with no significant risk increase.

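### Section 14.2 appears to benchmark device-related severe events against a 0.35% major-complication rate, and with no safety interval planned a zero count in at most 47 subjects could be misread as comparability

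*Combined protocol and SAP*

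**What the plan says.** Section 14.2 plans two safety outputs.

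- The first has no attribution filter: "The incidence of major complications using the MCS and the Standard Optical Colonoscopy will be presented".
- The second is device-attributed and severity-graded: the "rate of MCS -related severe adverse events as compared to standard colonoscopy procedure will be evaluated".

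The next sentence of 14.2 supplies the only reference figure, an "overall low risk of major complications of approximately 0.35 percent" for routine colonoscopy, citing two literature sources. Section 4.7 uses the same 0.35% when it expects procedural risk with the MCS to be comparable to that of a conventional colonoscope. Section 4.2 states that "the complications associated with using the MCS cannot be differentiated from those associated with the colonoscopy procedure".

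Section 16.2 defines severe as an intensity grade: a marked effect on activity, or a need for medical care. The documents do not itemise major complications.

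Section 15.2.3 specifies listings, counts and percentages for adverse events, over every enrolled subject. It names no confidence interval. Intervals at 95% are planned for the cleansing rate (15.2.2) and for cecal intubation (15.2.4).

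**The concern.** The two sides of the second comparison differ in two ways. The trial side counts events by intensity grade, whereas the reference counts major complications. The trial side also keeps only events attributed to the MCS, whereas the reference covers the whole procedure, and section 4.2 says that this attribution cannot be separated. Counting only attributed events lowers the MCS rate. The broad severe grade, which includes any event needing medical care, can raise it.

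The second difficulty is precision. Zero events is the most likely result here even if the true risk is twice the reference. Without an interval, the report would show 0% beside 0.35%, in a document whose section 4.7 already expects comparable risk. A reader could take that as confirmation although the data would be compatible with far higher rates.

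**Working it through.** **Inputs.** Reference rate p0 = 0.0035 (14.2, 4.7). Enrolment up to 47 (11.1, 15.1). Single arm (synopsis, section 10). Safety set: all enrolled (15.2.3).

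**The plan's own figure.** The only sample-size calculation is for cleansing. McNemar, with discordant proportions 0.6 and 0, power 0.80 and alpha 0.05 taken as two-sided:

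n = (1.960·√0.6 + 0.842·√(0.6 − 0.36))² / 0.36 = 10.35, so 11 pairs, as stated.

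The listed parts give 9 + 33 + 4 = 46, and 42/0.9 = 46.7 rounds up to 47. No calculation addresses safety, and the 0.35% is a literature value that cannot be rederived from the documents.

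**Number exposed.** Subjects count as enrolled from the eligibility visit (12.2), and those who do not complete the preparation do not undergo the procedure (12.5). Some enrolled subjects may therefore never be exposed. As an assumption I use 47, 43 (47 − 4 planned withdrawals) and 42 (9 + 33).

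**Chance of zero events**, (1 − p)^n:

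| True rate | n = 47 | n = 42 |
|---|---|---|
| 0.35% | 0.9965^47 = 85% | 86% |
| 0.70% (2×) | 0.993^47 = 72% | 74% |
| 1.75% (5×) | 0.9825^47 = 44% | 48% |
| 3.5% (10×) | 0.965^47 = 19% | 22% |

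Expected events at the reference rate: 47 × 0.0035 = 0.16.

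**Upper limit after zero events**, exact two-sided 95%, 1 − 0.025^(1/n):

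- n = 47: 7.5%, and 0.0755/0.0035 = 21.6 times the reference
- n = 43: 8.2%, 23.5 times
- n = 42: 8.4%, 24.0 times

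**One or two events** (Clopper-Pearson, n = 47):

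- 1/47 = 2.1%, interval 0.05% to 11.3%, which includes 0.35%.
- 2/47 = 4.3%, interval 0.52% to 14.5%, which excludes 0.35%.
- The chance of two or more events is 1.2% at a true rate of 0.35% and 49% at 3.5%.

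On like-for-like events the comparison could therefore signal a much higher rate, but a zero count could not show similarity.

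**Denominator effect.** One event is 1/47 = 2.1% or 1/42 = 2.4%, so dilution by unexposed subjects is small.

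**The case against.** The strongest reply is that 14.2 already plans the like-named comparison, since major complications are to be presented for both settings without an attribution filter. That stands. It would be wrong to infer that the device-attributed rate is the only comparison planned. That it is set against 0.35% is itself inferred from its placement in 14.2, from 4.7 and from the absence of any other reference. What remains is that the second comparison is also promised, and that neither output has an interval.

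A reader might also infer that the plan intends to conclude comparability. It does not. There is no safety test, margin or rule, section 15.1 calls the study a pilot, and the wording in 4.7 is a pre-trial expectation. Nor does participant protection rest on this comparison: section 4.6 stops the study pending DSMB investigation "in case of occurrence of a SAE at least possibly related to the MCS".

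Three further stronger readings fail.

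- A bias in favour of the device cannot be claimed, because the two differences can pull in opposite directions. The event definition behind 0.35% may be given in the cited sources, which are not part of the documents.
- Bleeding appears in 14.2 among expected non-severe events ("gas and in some cases bleeding") and in 4.2 as a colonoscopy risk. This is not a contradiction, because one event type can occur at several severities.
- Section 14.2 does not name the relationship grades that count as MCS-related. This is missing detail rather than lost information, because rates are summarised by severity and relationship and a reader can apply either cut-off.

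**Conclusion.** The concern holds as a weakness of interpretation, with a cheap remedy. The severe-event comparison, as its placement implies, mixes event classes and attribution, in an unknown direction. The plan gives no interval for any safety rate.

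Zero events is the most likely result both at 0.35% (85%) and at twice that rate (72%). The corresponding upper limit is 7.5% with 47 exposed, or about 8.2% to 8.4% with 43 or 42. A zero count therefore cannot support comparability. Two or more events would be informative: 2/47 excludes 0.35%.

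These figures assume independent subjects, at most one counted event per subject, and the exposed numbers stated. The inclusion of unexposed subjects in the denominator is a minor matter.

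**What to change.** **In 14.2:**

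- Make the already planned major-complication incidence the only rate set against 0.35%. Count it regardless of device attribution, with the events listed in advance and matched to the definition in the sources cited for that figure.
- Report MCS-related severe adverse events separately, without that benchmark.
- State that the comparison is descriptive and cannot support a conclusion of comparability.

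**In 15.2.3:**

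- Give both rates with exact 95% confidence intervals, over subjects in whom the MCS was inserted or attempted. Include the learning-curve subjects, whom section 14 already keeps in the safety evaluation, and use the actual number exposed.
- Keep the all-enrolled set for overall and preparation-related adverse events.

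**Cost.** Revised wording, one event list and two intervals, with no new data. The safety statement becomes less favourable, because a zero count will carry an upper limit of about 7.5% or more.

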### **Specific situations occurring during colonoscopy**

- If the attempt to reach the cecum is failed, the investigator shall perform the procedure with a pediatric or any other colonoscope he/she may choose without the MCS. The subject will complete the study as planned.
- If a medical condition requiring treatment is detected during colonoscopy, the subject will be treated as per the standard care.

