#### 15.2.3. SECONDARY SAFETY ANALYSIS

The secondary endpoint is to evaluate the Device related adverse event and the overall adverse events rate.

The safety analysis set will consist of all subjects who were enrolled into the study.

Individual listings of adverse events including type of device, adverse events (reported term), seriousness, duration, relationship to the study device, severity and the adverse events outcome will be provided for the total population and per population group.

AEs will be summarized using frequency counts and percentages.

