## 16.2. ADVERSE EVENTS CLASSIFICATION

The severity of adverse events will be rated as follows:

- Mild: An AE which is transient or mild in nature, which does not limit the subject’s activity, and which does not require medical intervention
- Moderate: An AE which has mild-moderate impact on the subject’s activity or requires minimal medical intervention or monitoring
- Severe: An AE which has marked impact on the subject’s activity or requires medical care

Each AE will be classified as SAE or non-SAE as follows:

- A serious adverse event (SAE) is any adverse event that is fatal or life threatening, or results in permanent impairment of a body structure or function, or in-patient or prolonged hospitalization, or requires medical or surgical intervention to prevent life-threatening illness or injury, or led to foetal distress, foetal death or congenital abnormality or birth defect.

The relationship of the AE and SAE to the treatments or procedures is defined as follows:

- Unrelated: Any event that does not follow a reasonable temporal sequence from administration of study treatment AND that is likely to have been produced by the subject’s clinical state or other modes of therapy administered to the subject.
- Unlikely: Any event that does not follow a reasonable temporal sequence from administration of study treatment OR that is likely to have been produced by the subject’s clinical state or other modes of therapy administered to the subject OR that does not follow a known pattern

of response to suspected device OR does not reappear or worsen when the device is re-administered

- Possibly: Any reaction that follows a reasonable temporal sequence from administration of study treatment OR that follows a known response pattern to the suspected device AND that could not be reasonably explained by the known characteristics of the subject's clinical state or other modes of therapy administered to the subject.
- Related: Any reaction that follows a reasonable temporal sequence from administration of study treatment AND that follows a known response pattern to the suspected device AND that recurs with re-challenge, AND/OR is improved by stopping the use of the device.

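### Section 14.2 compares MCS-related severe adverse events with standard colonoscopy, but the only figure it gives for standard colonoscopy is an overall major-complication risk of about 0.35%, so the two sides are not like for like

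*Combined protocol and SAP*

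**What the plan says.** Section 14.2 makes three statements in sequence.

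- It first plans a presentation with no restriction by cause: "The incidence of major complications using the MCS and the Standard Optical Colonoscopy will be presented".
- It then names the measure on which MCS safety is judged: the "rate of MCS -related severe adverse events as compared to standard colonoscopy procedure will be evaluated".
- It then describes routine colonoscopy as having an "overall low risk of major complications of approximately 0.35 percent". This is the only risk figure for standard colonoscopy in the documents. Section 4.7 repeats it and applies it to the whole procedure carried out with the MCS.

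Four other places bear on the point.

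- Section 4.2 says that "the complications associated with using the MCS cannot be differentiated from those associated with the colonoscopy procedure".
- Section 16.2 grades an event as severe if it strongly affects the subject's "activity or requires medical care". The protocol does not define a major complication.
- Section 12.5 (specific situations) says that, after a failed attempt to reach the cecum, the investigator shall "perform the procedure with a pediatric or any other colonoscope he/she may choose without the MCS".
- Section 15.2.3 covers both the device-related and the overall adverse event rates in all enrolled subjects, and says that "AEs will be summarized using frequency counts and percentages".

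The study has a single arm, so any comparison with standard colonoscopy is with an external figure.

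**The concern.** The sentence that names the safety comparison differs from the adjacent figure in two respects.

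**Attribution.** The MCS side counts only events judged to be MCS-related. The 0.35% is described as an overall risk of the procedure. The comparison thus depends on a separation that section 4.2 says cannot be made. The switch of colonoscope in section 12.5 shows how this could matter: an injury recognised after the switch could be assigned to the second colonoscope and leave the compared count.

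**Grade.** The MCS side uses severe as defined in section 16.2, while the figure for standard colonoscopy concerns major complications.

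At stake is how the safety result reads. A rate restricted by attribution, set beside an overall procedure risk, can look reassuring partly because of how events were assigned.

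**Working it through.** **Inputs.** The enrolment ceiling is 47 (section 15.1) and the benchmark is 0.35% (sections 14.2 and 4.7). The share *f* of events that would be judged MCS-related is not in the documents, so it is assumed here and varied from 25% to 100%. For the arithmetic only, severe is treated as equal to major.

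**The plan's own figures.** Section 15.1 adds 9 + 33 + 4 = 46 and states up to 47; (9 + 33)/0.9 = 46.7 also rounds up to 47. The 0.35% is a literature figure and cannot be derived from the documents.

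**Effect of the attribution filter.** If the whole-procedure risk is *p*, the filtered rate is *f* × *p*. The whole-procedure risk that would read as 0.35% is therefore 0.35%/*f*. The last column is 1 − (1 − *f* × 0.0035)^47.

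| Assumed share *f* | Whole-procedure risk that reads as 0.35% | Filtered rate if the true risk is 0.35% | Chance of at least one counted event in 47 at that rate |
|---|---|---|---|
| 100% | 0.35% | 0.35% | 15.2% |
| 75% | 0.47% | 0.26% | 11.6% |
| 50% | 0.70% | 0.18% | 7.9% |
| 25% | 1.40% | 0.09% | 4.0% |

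As an illustration, take a doubled risk of 0.70% and *f* = 50%. The chance of any event in 47 subjects is 1 − (1 − 0.007)^47 = 28% unfiltered and 1 − (1 − 0.0035)^47 = 15% filtered. The filtered chance equals the unfiltered chance at benchmark risk. This rests on two assumptions, the doubled risk and the share.

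**Direction.** Against all severe events in the same subjects, the filter can only reduce the count. Against 0.35% the direction is not determined, for two reasons. Severe in section 16.2 may be broader than major, because needing medical care is enough. The documents also do not show whether the sources of the 0.35% applied an attribution rule of their own.

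**Precision, with or without the filter.** Limits are exact (Clopper-Pearson) and two-sided 95%.

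- At 0.35% and n = 47, the expected count is 47 × 0.0035 = 0.16, and the chance of none is 0.9965^47 = 85%.
- For 0/47 the upper limit is 1 − 0.025^(1/47) = 7.5%, about 22 times 0.35%.
- For 1/47 the rate is 2.1%, with limits 0.05% to 11.3%. Both intervals contain 0.35%, so the attribution of one event does not change what can be concluded.
- If the 4 planned withdrawals all occurred before the procedure (an assumption), n = 43. The expected count is 0.15, the chance of none is 86%, and 0/43 gives 0 to 8.2%.
- For the upper limit to fall to 0.35% with no events, n must reach ln(0.025)/ln(0.9965) = 1,052.1, so 1,053 procedures.

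**The case against.** The best defence is that the plan already contains the right figure. The sentence before the named comparison presents major complications for both procedures without any filter, and it uses the same term as the 0.35%. Section 15.2.3 adds the overall adverse event rate and individual listings with severity and relationship, so in at most 47 subjects nothing is hidden. This stands. It rules out any claim that unfiltered data are missing or that section 15.2.3 is at fault. It does not repair the sentence that names the evaluation, which still uses the filtered rate.

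Second, no sentence says explicitly that the MCS-related rate will be set against 0.35%. That is also correct: the pairing follows from the order of the text and from the absence of any other figure for standard colonoscopy.

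Third, the share *f* is assumed and could be close to 100%. If device and procedure effects cannot be separated, assessors may have little basis for ruling the MCS out. Section 14.2 does not say which relatedness categories count, and section 4.6 uses at least possibly related as its trigger for stopping the study. At *f* = 100% the attribution gap disappears. This stands as a limit on the size of the effect.

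A reader might infer more: that the comparison is biased in the device's favour against 0.35%, or that it would conceal a doubled risk. The documents do not support either. The severe-versus-major difference and the unseen sources leave the net direction open, and the doubled-risk figures are illustrative only.

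Lastly, a device-related rate suits the secondary objective of evaluating safety related to the MCS. That is a reason to keep reporting it, but not to set it beside an overall procedure risk.

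**Conclusion.** The point holds in a limited form. The measure that section 14.2 names for comparison with standard colonoscopy is restricted by attribution and graded severe, while the only figure available for the other side is an overall major-complication risk. The quantities differ, and section 4.2 undercuts the restriction. The filter lowers the count relative to all severe events in these subjects by an amount the documents do not give; the net direction against 0.35% is unknown.

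The severity is minor. The safety analysis is counts and percentages, with no test, margin or success criterion on this comparison. At 47 subjects the interval is far too wide to judge 0.35% on either basis, so the corrected comparison would be descriptive too.

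**What to change.** In section 14.2:

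- Make the comparison with standard colonoscopy on the incidence of all major complications regardless of attribution, which the preceding sentence already plans to present.
- Take as denominator the subjects who underwent the procedure with the MCS inserted, and count events that follow a switch to another colonoscope. State that this denominator differs from the all-enrolled safety set in section 15.2.3, which can include subjects who never reached the procedure. Section 15.2.3 itself can stay as it is.
- Report the incidence with an exact 95% interval and call the comparison descriptive.
- Keep the MCS-related severe adverse event rate as a separate output that is not compared with 0.35%.

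Listing the events that count as major complications would help, but that is missing detail rather than part of this point.

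The cost is a change of wording in section 14.2 and one confidence interval, with no new data and no change in sample size. The downside is that the headline rate may look less favourable. It will also include ordinary colonoscopy complications, so it will not isolate the effect of the device.
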